## 10.2 Additional Analysis

[figure not shown]
Qualifying prodrome events and prodrome symptom data collected in the screening period will be analyzed for the screened population to understand the prodrome information in the general population.

For each participant, number of qualifying prodrome events and positive prodrome events will be summarized. The positive prodrome event rate will be calculated based on the denominator of the number of qualifying prodrome events and the numerator of the number of positive prodrome events. The positive prodrome event rate will be analyzed using a GLMM model with participant as a random effect. The LSMEAN of the positive prodrome rate with 95% CI will be reported.

[figure not shown]
Prodrome symptoms will be analyzed in individual prodrome symptom positive rate. The individual prodrome symptoms positive rate is to show how likely an individual qualifying prodrome event with this symptom at baseline will be positive. The individual prodrome symptom positive rate will be calculated based on the denominator of the numbers of qualifying prodrome events with this symptom and the numerator of the numbers of positive qualifying prodrome events preceded with this symptom. Individual prodrome symptom prevalence rate will be calculated based on the denominator of the numbers of qualifying prodrome events and the numerator of the numbers of qualifying prodrome events preceded with this symptom. These participant-specific variables will then be summarized in the screened population who have entered eDiary data in the screening period. The individual prodrome symptom positive rate in the screening period will also be analyzed in the mITT population. In addition, Kaplan-Meier curves for time to onset of a headache of any intensity and time to onset of a headache of moderate/severe intensity using all prodrome events and using the first prodrome event will be generated.

The derivation of the endpoints in the screening period are the same as double-blind period except for the absence of moderate/severe headache which are described in [Figure 8](#), [Figure 9](#), and [Figure 10](#).

[figure not shown]
**Figure 8. Determination of absence of moderate/severe headache within 24 hrs in the screening period (responder)**

**Figure 9. Determination of absence of moderate/severe headache within 48 hours in the screening period (responder)**

**Figure 10. Determination of absence of moderate/severe headache by T hours (1, 2, 3, 4, 6, 8 hours) in the screening period (responder)**

## 11.0 Interim Analyses

No interim analysis of unblinded data is planned for this study.

## 11.1 Data Monitoring Committee

Data monitoring committee is not required for this study.

## 12.0 Overall Type-I Error Control

To control the family-wise type I error rate at 0.05 for multiplicity across the hypothesis tests in the primary and secondary analyses, a hierarchical gatekeeping procedure will be followed.

Step 1: Test the primary hypothesis. If p-value <0.05, reject the primary hypothesis and go to the Step 2, otherwise stop.

Step 2: Test the first secondary hypothesis. If the first secondary hypothesis is rejected, go to Step 3, otherwise stop.

Step 3: Test the second secondary hypothesis. If 2nd secondary hypothesis is rejected, go to test third secondary hypothesis, otherwise stop.

Step 4: Test the third secondary hypothesis.

## 13.0 SAP Version History

This Statistical Analysis Plan (SAP) for Study 3110-304-002 is based on the Protocol Amendment 2 dated 02 May, 2020.

SAP Version History Summary			
SAP Version	Approval Date	Change	Rationale
1	01 February 2021	Not Applicable	Original version

SAP Version History Summary			
SAP Version	Approval Date	Change	Rationale
2	03 May 2022	Updated the additional prodrome endpoints as: 
 
• Absence of 5 most common individual prodrome symptoms of any intensity at each timepoint
 
• Absence of 5 most common individual moderate/severe prodrome symptoms at each timepoint
 
• Absence of 5 most common individual severe prodrome symptoms at each timepoint
 
	Protocol Amendment 1. The 5 most common prodrome symptoms are mostly meaningful.
		Updated the additional nonheadache migraine symptom endpoints as: 
 
• Absence of nonheadache migraine symptoms (photophobia, phonophobia, nausea, dizziness) of any intensity on or after any intensity headache start at each timepoint
 
• Absence of moderate/severe nonheadache migraine symptoms (photophobia, phonophobia, nausea, dizziness) on or after any intensity headache start at each timepoint
 
• Absence of severe nonheadache migraine symptoms (photophobia, phonophobia, nausea, dizziness) on or after any intensity headache start at each timepoint
 
	Protocol Amendment 1. Nonheadache migraine symptom is collected on or after any intensity headache collected in eDiary.
		Updated the additional time to prodrome symptom endpoint as: 
 
• Time to absence of 5 most common individual prodrome symptoms
 
	Protocol Amendment 1. The 5 most common prodrome symptoms are mostly meaningful.

SAP Version History Summary			
SAP Version	Approval Date	Change	Rationale
		Updated the sensitivity analysis 3 so that the missing event due to lack of prodrome is imputed under MAR, and imputed under MNAR for other reasons	Discontinuation due to all other reasons is considered as MNAR except lack of prodrome
		Updated sample size from 600 randomized to 516 randomized	Protocol Amendment 1. Sample size is reduced due to lower percentage of participants who have indeterminable data
		Updated the secondary and additional headache endpoints derivation in Figure 4 , Figure 5 , Figure 6 , and Figure 7	Updated based on the below assumptions: 1. Missing headache at 48 hours will lead to the endpoint within 48 hours indeterminable. 2. When 24 hours recall headache is collected, the missing headache intensity at prespecified hours before 24 hours recall headache time is assumed less severe than the 24 hours recall headache intensity.
		Added the derivation of absence of moderate/severe headache in the screening period in Figure 9 and Figure 10	The derivation of absence of moderate/severe headache in the screening period is difference from those in the DB period.
		Added analysis related COVID vaccine	COVID vaccine is collected in CRF
		Re-order secondary endpoints	Protocol Amendment 2
		Additional endpoint changed from absence of aura by timepoint to absence of aura at each timepoint	Protocol Amendment 2
		3	10 May 2022
		Added predose baseline variable in the	Predose baseline effect

SAP Version History Summary			
SAP Version	Approval Date	Change	Rationale
		analysis models of absence of any intensity, moderate/severe intensity, severe intensity for the 5 most common individual prodrome symptom, and absence of aura at each timepoint	should be controlled in the analysis model

## **15.0 Appendices**

### **Appendix A. Protocol Deviations**

Protocol deviations will be defined in Protocol Deviation Requirement Specification, including importance classification. The number and percentage of participants with significant protocol deviations that occurred in the double-blind treatment period will be summarized by treatment sequence for the ITT population.

## **Appendix B. Definition of Adverse Events of Special Interest**

The following AESI(s) have been specified in the protocol and will be reported:

- Treatment-emergent suicidal ideations with intent, with or without a plan, (i.e., Type 4 or 5 on the C-SSRS) or any suicidal behaviors.
- Potential Hy's law cases: elevated ALT or AST laboratory value that is  $\geq 3 \times$  ULN and an elevated total bilirubin laboratory value that is  $\geq 2 \times$  ULN and, at the same time, an alkaline phosphatase laboratory value that is  $< 2 \times$  ULN.

Responses to the C-SSRS that meet the above criterion will be captured in the eTablet and monitored by the sponsor.

## Appendix C. Potentially Clinically Important Criteria for Safety Endpoints

The potentially clinically significant criteria for clinical laboratory parameters, vital signs and ECG parameters are provided in the following tables.

**Clinical laboratory** parameters are provided in the following tables.

**Table C-1. Potentially Clinically Significant Criteria for Clinical Laboratory Parameters**

Category	Parameter	SI Unit	PCS Criteria	
			PCS Low	PCS High
Chemistry	Albumin	g/L	$< 0.8 \times \text{LLN}$	$> 1.2 \times \text{ULN}$
	Alanine aminotransferase	U/L	—	$\geq 3.0 \times \text{ULN}$
	Alkaline phosphatase	U/L	—	$\geq 3.0 \times \text{ULN}$
	Aspartate aminotransferase	U/L	—	$\geq 3.0 \times \text{ULN}$
	Bicarbonate	mmol/L	$< 0.9 \times \text{LLN}$	$> 1.1 \times \text{ULN}$
	Bilirubin, total	$\mu\text{mol/L}$	—	$\geq 1.5 \times \text{ULN}$
	Blood urea nitrogen	mmol/L	—	$> 1.5 \times \text{ULN}$
	Calcium	mmol/L	$< 0.9 \times \text{LLN}$	$> 1.1 \times \text{ULN}$
	Chloride	mmol/L	$< 0.9 \times \text{LLN}$	$> 1.1 \times \text{ULN}$
	Cholesterol, total	mmol/L	—	$> 1.6 \times \text{ULN}$
	Creatinine	$\mu\text{mol/L}$	—	$> 1.5 \times \text{ULN}$
	Creatine kinase	U/L	—	$> 2.0 \times \text{ULN}$
	Estimated glomerular filtration rate	$\text{mL/min}/1.73\text{m}^2$	$< 0.8 \times \text{LLN}$	—
	Glucose, nonfasting	mmol/L	$< 0.8 \times \text{LLN}$	$> 2.0 \times \text{ULN}$
	Lactate dehydrogenase (LDH)	U/L	—	$> 3.0 \times \text{ULN}$
	Phosphorus	mmol/L	$< 0.9 \times \text{LLN}$	$> 1.1 \times \text{ULN}$
	Potassium	mmol/L	$< 0.9 \times \text{LLN}$	$> 1.1 \times \text{ULN}$
	Protein, total	g/L	$< 0.9 \times \text{LLN}$	$> 1.1 \times \text{ULN}$
	Sodium	mmol/L	$< 0.9 \times \text{LLN}$	$> 1.1 \times \text{ULN}$
	Triglycerides	mmol/L	—	$> 2.0 \times \text{ULN}$
Uric acid	$\mu\text{mol/L}$	—	$> 1.2 \times \text{ULN}$	

Category	Parameter	SI Unit	PCS Criteria	
			PCS Low	PCS High
Hematology	Basophils, absolute cell count	10  /L	—	> 2.0 × ULN
	Eosinophils, absolute cell count	10  /L	—	> 2.0 × ULN
	Hematocrit	Ratio	< 0.9 × LLN	> 1.1 × ULN
	Hemoglobin	g/L	< 0.9 × LLN	> 1.1 × ULN
	Lymphocytes, absolute cell count	10  /L	< 0.7 × LLN	> 1.3 × ULN
	Monocytes, absolute cell count	10  /L	< 0.5 × LLN	> 2.0 × ULN
	Neutrophils, absolute cell count	10  /L	< 0.7 × LLN	> 1.3 × ULN
	Platelet count	10  /L	< 0.5 × LLN	> 1.5 × ULN
	Red blood cell count	10  /L	< 0.9 × LLN	> 1.1 × ULN
	White blood cell count	10  /L	< 0.9 × LLN	> 1.5 × ULN
Urinalysis	pH	pH	< 0.9 × LLN	> 1.1 × ULN
	Glucose	mmol/L	—	Positive 
	Protein	g/L	—	Positive 
	Specific gravity	—	—	> 1.1 × ULN

LLN = lower limit of normal value; ULN = upper limit of normal value; normal value provided by laboratory;

SI = Le Système International d'Unités (International System of Units)

- Any results other than trace or normal will be considered as positive.
- Any results other than trace or negative will be considered as positive.

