10.2. Appendix 2: Clinical Laboratory Tests

- The tests detailed in Table 10-1 will be performed by the central laboratory.
- Protocol-specific requirements for inclusion or exclusion of participants are detailed in Section 5 of the protocol.
- Additional tests may be performed at any time during the study as determined necessary by the investigator or required by local regulations.
- Investigators must document their review of each laboratory safety report.

Table 10-1 Protocol-required Clinical Laboratory Tests

Category	Parameter
Chemistry	Sodium, potassium, chloride, bicarbonate, glucose, blood urea nitrogen, creatinine, total bilirubin, alkaline phosphatase, AST, ALT, lactate dehydrogenase, creatine kinase, total protein, albumin, calcium, phosphorus, uric acid, total cholesterol, high density lipoprotein, low density lipoprotein, total triglycerides. The estimated glomerular filtration rate will be calculated by the central laboratory.
Hematology	Hemoglobin; hematocrit; red blood cell count; red blood cell indices (mean corpuscular volume, mean corpuscular hemoglobin, mean corpuscular hemoglobin concentration); white blood cell count, including differential (neutrophils, lymphocytes, monocytes, eosinophils, and basophils); platelet count
Urinalysis	Urine dipstick for specific gravity, pH, protein, glucose, ketones, bilirubin, and blood; microscopic exam including red blood cells/high-power field, white blood cells/high-power field, and casts/low-power field.
Coagulation	At Visit 1 only: INR
Urine Drug Screen	Screening for drugs of abuse (eg, marijuana, cocaine, phencyclidine, amphetamines, benzodiazepines, barbiturates, opiates) will be conducted using a urine drug screen at Visit 1. Urine drug screens positive for recreational (including marijuana regardless of legality) or illicit drugs or nondisclosed concomitant medications are allowed to be repeated. Further urine drug screens may be repeated with permission from the sponsor; a negative result or an explanation of a positive result due to concomitant medication use (eg, opioids prescribed for migraine pain) will be required for randomization.

Refer to Section 10.3 for information regarding clinical laboratory tests for AESIs.

10.3. Appendix 3: Adverse Events: Definitions and Procedures for Recording, Evaluating, Follow-up, and Reporting

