### **9.3 Analysis of Laboratory Data**

#### **9.3.1 Clinical Laboratory Parameters**

Descriptive statistics for clinical laboratory values (in SI units) at baseline and changes from baseline at each assessment time point will be presented by study intervention for

each clinical laboratory assessment. An assessment will be assigned to the most recently administered study intervention.

- Hematology: Hemoglobin; hematocrit; red blood cell count; red blood cell indices (mean corpuscular volume, mean corpuscular hemoglobin, mean corpuscular hemoglobin concentration); white blood cell count, including differential (neutrophils, lymphocytes, monocytes, eosinophils, and basophils); platelet count
- Chemistry: Sodium, potassium, chloride, bicarbonate, glucose, blood urea nitrogen, creatinine, total bilirubin, alkaline phosphatase, aspartate aminotransferase, alanine aminotransferase, lactate dehydrogenase, creatine kinase, total protein, albumin, calcium, phosphorus, uric acid, total cholesterol, HDL, LDL, total triglycerides, eGFR (calculated by the central lab)
- Urinalysis: Specific gravity, pH.

Shift tables from baseline to end of study for these clinical laboratory parameters will be presented by study intervention for the following categories: low, normal, and high, which are categorized by the laboratory vendor based on reference ranges.

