### **9.3.2 Potentially Clinically Significant Laboratory Findings**

Clinical laboratory test values will be considered potentially clinically significant (PCS) if they meet either the lower-limit or higher-limit PCS criteria listed in Table C-1.

The number and percentage of participants who have at least one PCS post-baseline clinical laboratory value will be tabulated by study intervention. The percentages will be calculated based on the denominator of the number of participants with available non-PCS baseline values and at least one post-baseline value and the numerator of the number of participants with non-PCS baseline value and at least one PCS post-baseline value. In addition, a listing of all AEs occurring in participants who have PCS clinical laboratory test values will be provided.

A listing of participants with PCS postbaseline values will be provided for the safety population.

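### The only potentially clinically significant (PCS) criterion for urine specific gravity in SAP Table C-1, above 1.1 times the upper limit of normal, cannot be met by any urine reading

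*SAP*

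**What the plan says.** SAP 9.3.2 calls a laboratory value PCS "if they meet either the lower-limit or higher-limit PCS criteria listed in Table C-1". It tabulates PCS results by study intervention, with "the numerator of the number of participants with non-PCS baseline value and at least one PCS post-baseline value" as the numerator of each percentage. It also provides a listing of participants with PCS values and a listing of the adverse events in those participants.

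For urine specific gravity, Table C-1 reads "Specific gravity — — > 1.1 × ULN". The two dashes are the unit and the PCS-low cell, so the high limit is the only route to a flag. The table note says that the limits of normal are supplied by the laboratory ("normal value provided by laboratory"); no figure is printed.

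Protocol Table 10-1 (Appendix 2) gives the method of measurement: "Urine dipstick for specific gravity, pH, protein, glucose, ketones, bilirubin, and blood". SAP 9.3.1 names the parameter for analysis ("Urinalysis: Specific gravity, pH") and plans descriptive statistics, changes from baseline and low/normal/high shift tables for it by study intervention.

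Neither document gives specific gravity a second cut-off, or says that the multiplier applies to the excess over 1.000 and not to the whole number.

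**The concern.** A multiplier of the ULN makes sense for a quantity measured from zero, such as an enzyme activity or a cell count. Specific gravity is anchored at 1.000, the value of water, and urine differs from water only in the second and third decimals. Taking 10% of the whole number adds at least 0.100, which is larger than the whole range over which urine varies.

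A prespecified safety criterion that no result can meet tests nothing. Its count is zero for ubrogepant and for placebo whatever the drug does to the urine. A reader of the PCS output could not tell that structural zero from a real absence of abnormal values.

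**Working it through.** The plan states the criterion only as a multiple of a limit that it does not print, so there is no absolute cut-off to reproduce. The check is to compute what the multiple implies.

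**Inputs**
- Multiplier 1.1, high side only: SAP Table C-1.
- ULN: not in the documents. Assumed 1.020 to 1.050, with 1.000 (water) as the floor.
- Highest specific gravity that urine can give: not in the documents. Assumed 1.030 to 1.050, with 1.080 as a stress value.

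**Step 1. The cut-off, 1.1 × ULN**

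| ULN | Cut-off |
|---|---|
| 1.000 (floor) | 1.1 × 1.000 = 1.100 |
| 1.020 | 1.1 × 1.020 = 1.122 |
| 1.025 | 1.1 × 1.025 = 1.1275 |
| 1.030 | 1.1 × 1.030 = 1.133 |
| 1.035 | 1.1 × 1.035 = 1.1385 |
| 1.040 | 1.1 × 1.040 = 1.144 |
| 1.050 | 1.1 × 1.050 = 1.155 |

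Every cut-off, including the one at the floor, lies above 1.080.

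**Step 2. The inverse: the ULN at which a flag becomes possible.** A maximum reading M exceeds the cut-off only if ULN < M / 1.1.

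| Maximum reading M | ULN would have to be below |
|---|---|
| 1.030 | 1.030 / 1.1 = 0.936 |
| 1.040 | 1.040 / 1.1 = 0.945 |
| 1.050 | 1.050 / 1.1 = 0.955 |
| 1.080 | 1.080 / 1.1 = 0.982 |

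All four limits are below 1.000. An upper limit of normal for urine cannot be lighter than water, so no admissible ULN makes the criterion reachable.

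**Step 3. How far out the criterion sits.** With an ULN of 1.030, a normal sample may exceed water by up to 1.030 − 1.000 = 0.030. The criterion requires an excess above 1.133 − 1.000 = 0.133. The ratio is 0.133 / 0.030 = 4.4.

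**Step 4. Consequence under SAP 9.3.2.** With no low limit and an unreachable high limit, the numerator is 0 under both treatments for every ULN in the range. Only a recording or unit error could produce a flag, for example 1030 entered against an ULN of 1.030.

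**The case against.** Four points can be made on the other side.

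*The figures come from outside the documents.* This is true of the ULN and of the urine maximum, and both are treated as assumptions with a range. The result does not depend on where in those ranges the true values lie. It needs only an ULN of at least 1.000, which follows from the scale, and a urine maximum not above 1.100.

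*Other parts of the plan cover specific gravity.* This stands, and it limits the harm. SAP 9.3.1 reports descriptive statistics, change from baseline and shifts between low, normal and high. Protocol 8.2.4 has the investigator assess every value outside the reference range and record clinically relevant changes as adverse events. Specific gravity is not an adverse event of special interest and enters no efficacy analysis. Post-dose urinalysis is scheduled only at Visit 4 or early termination, so the PCS row would carry little weight even with a good cut-off.

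*The report need not show a misleading 0%.* A reader might infer that the safety table will print a row of zeros and present it as reassurance. The documents do not go that far: SAP 1.0 puts table specifications in a separate document, and rows without a PCS value may simply not be printed. What can be said is that nobody will be flagged, and that neither a zero nor a missing row is evidence of normal results.

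*Urine pH.* A reader might infer that the PCS-low limit for urine pH, below 0.9 times the lower limit of normal, has the same fault. The documents do not support this. It would depend on the laboratory's lower limit and on the lowest reading of its strip, and neither is given. The pH row also has a high criterion that nothing here calls into question.

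**Conclusion.** The criterion is wrong as written. For urine specific gravity, a cut-off of 1.1 × ULN is at least 1.100, and 1.122 to 1.155 for assumed ULNs of 1.020 to 1.050. That is above an assumed urine maximum of 1.030 to 1.050, and above 1.080 as a stress value. Barring recording errors, the number of participants flagged on this parameter is zero under both treatments by construction.

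The point is minor. It affects one row of the PCS tabulation and the matching entries in the listings. Efficacy, hepatic monitoring and the other laboratory criteria are not involved, and information on specific gravity is still reported through SAP 9.3.1.

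**What to change.** Delete the specific gravity row from Table C-1 and rely on the low/normal/high shift table already planned in SAP 9.3.1. This needs no new threshold and loses nothing, since the row cannot flag anyone.

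If a PCS criterion is wanted, replace the cell with one that the sponsor has checked against the central laboratory's dipstick scale. A value above the ULN is a candidate, but only if the scale extends beyond the ULN. With an ULN of 1.035 and a strip that ends at 1.030, for instance, it too could never be met. Where it is attainable it will flag some unimportant values, and it largely repeats the high category of the shift table. Table C-1 already uses a positive result in place of a multiplier for urine glucose and protein, so a criterion suited to the scale would not be out of style.

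The cost is one row or one cell of a SAP table and the matching output specification. Trial conduct, participants and the type I error plan are unaffected.

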**Table C-2. Criteria for Hepatic Laboratory Abnormalities**

Laboratory Parameter	Categories
ALT	≥ 1 × ULN
	≥ 1.5 × ULN
	≥ 2 × ULN
	≥ 3 × ULN
	≥ 5 × ULN
	≥ 10 × ULN
	≥ 20 × ULN

Laboratory Parameter	Categories
AST	$\geq 1 \times \text{ULN}$
	$\geq 1.5 \times \text{ULN}$
	$\geq 2 \times \text{ULN}$
	$\geq 3 \times \text{ULN}$
	$\geq 5 \times \text{ULN}$
	$\geq 10 \times \text{ULN}$
	$\geq 20 \times \text{ULN}$
ALT or AST	$\geq 1 \times \text{ULN}$
	$\geq 1.5 \times \text{ULN}$
	$\geq 2 \times \text{ULN}$
	$\geq 3 \times \text{ULN}$
	$\geq 5 \times \text{ULN}$
	$\geq 10 \times \text{ULN}$
	$\geq 20 \times \text{ULN}$
Bilirubin Total	$\geq 1 \times \text{ULN}$
	$\geq 1.5 \times \text{ULN}$
	$\geq 2 \times \text{ULN}$
	$\geq 3 \times \text{ULN}$
	$\geq 5 \times \text{ULN}$
	$\geq 10 \times \text{ULN}$
	$\geq 20 \times \text{ULN}$
Alkaline Phosphatase	$\geq 1 \times \text{ULN}$
	$\geq 1.5 \times \text{ULN}$
	$\geq 2 \times \text{ULN}$
	$\geq 3 \times \text{ULN}$
	$\geq 5 \times \text{ULN}$
	$\geq 10 \times \text{ULN}$
	$\geq 20 \times \text{ULN}$
Concurrent Elevations 	ALT or AST $\geq 3 \times \text{ULN}$ and Bilirubin Total $\geq 1.5 \times \text{ULN}$
	ALT or AST $\geq 3 \times \text{ULN}$ and Bilirubin Total $\geq 2 \times \text{ULN}$

Laboratory Parameter	Categories
Potential Hy's Law 	ALT or AST $\geq 3 \times$ ULN and Bilirubin Total $\geq 2 \times$ ULN and ALP $< 2 \times$ ULN

ALT = alanine aminotransferase; AST = aspartate aminotransferase; TBL = total bilirubin; ALP = alkaline phosphatase; ULN = upper limit of normal (value provided by the laboratory)

1. Elevations are from the same day.

**Vital sign** values will be considered PCS if they meet both the observed value criterion and the change from baseline value criterion, if both criteria are available, or meet either the observed value criterion or the change from baseline value criterion that is detailed in the following table.

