8.2.4. Clinical Safety Laboratory Assessments

- See Section 10.2 for the list of clinical laboratory tests to be performed and the SoA (Section 1.3) for the timing and frequency. Hematology, chemistry, urinalysis, and urine pregnancy tests will be conducted at the Screening Visit (Visit 1), Randomization Visit (Visit 2), and Posttreatment/ET Visit (Visit 4). Coagulation, and the urine drug screen will be conducted at the Screening Visit (Visit 1) only.
- The investigator or subinvestigator will assess the clinical significance of any values outside the reference ranges provided by the laboratory, and participants with abnormalities judged to be clinically significant will be screen failed or withdrawn from the study.

- Positive results on the urine drug screen (unless explained by previously reported concomitant medication use, such as opioids prescribed for migraine pain) will be excluded from the study.
- A positive pregnancy test at Visit 1 or Visit 2 will exclude the participant from participation in the study. Participants who are confirmed to be pregnant during the study will be withdrawn.
- The investigator must review the laboratory report, document this review, and record any clinically relevant changes occurring during the study in the AE section of the eCRF. The laboratory reports must be filed with the source documents. Clinically significant abnormal laboratory findings are those that are not associated with the underlying disease, unless judged by the investigator to be more severe than expected for the participant's condition.
- All laboratory tests with values considered clinically significant during participation in the study or within 30 days after the last dose of study intervention should be repeated until the values return to normal or baseline or are no longer considered clinically significant by the investigator.
 - If such values do not return to normal/baseline within a period of time judged reasonable by the investigator, the etiology should be identified and the sponsor notified.
 - All protocol-required laboratory assessments, as defined in Section 10.2, must be conducted in accordance with the laboratory manual and the SoA (Section 1.3) or laboratory manual.

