9.4.2. Safety Analyses

The safety analysis will be performed using the safety population and will be fully defined in the SAP. The safety parameters will include AEs, clinical laboratory tests, ECGs, vital signs, and the C-SSRS. For each of the clinical laboratory tests, vital signs, and ECG parameters, the last nonmissing safety assessment before the first dose of double-blind study intervention will be used as the baseline for all analyses of that safety parameter.

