9.4.2.6. Potential Hy's Law

Potential Hy's Law criteria within a 24-hour window is defined by elevated ALT or AST laboratory value that is $\geq 3 \times ULN$ and an elevated total bilirubin laboratory value that is $\geq 2 \times ULN$ and, at the same time, an alkaline phosphatase laboratory value that is $< 2 \times ULN$, all based on blood draws collected within a 24-hour period.

Potential Hy's Law criteria without time window (evaluation of drug-induced serious hepatotoxicity) is defined by maximum of postbaseline elevation of ALT or AST laboratory

value that is $\geq 3 \times ULN$, along with maximum of postbaseline total bilirubin laboratory value that is $\geq 2 \times ULN$.

Participants who meet the potential Hy's Law criteria after taking study intervention and to the end of study participation will be summarized. If participants have unscheduled laboratory results after Visit 4 that meet potential Hy's Law criteria, the participants will be included in analysis. Supportive tabular displays will also be provided.

Participants who meet the potential Hy's Law criteria will be summarized by study treatment. The assessment will be present in the last study treatment the participant received.

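### SAP Table C-2 has no row for the protocol's no-time-window potential Hy's law definition, and the SAP does not record the omission

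*SAP*

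**What the plan says.** Protocol section 9.4.2.6 gives two definitions and says that participants who meet the criteria will be summarised.

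- **Within a window.** ALT or AST at least 3 x ULN, total bilirubin at least 2 x ULN and alkaline phosphatase (ALP) below 2 x ULN, "all based on blood draws collected within a 24-hour period".
- **Without a window.** "Potential Hy's Law criteria without time window (evaluation of drug-induced serious hepatotoxicity) is defined by maximum of postbaseline elevation" of ALT or AST to at least 3 x ULN, "along with maximum of postbaseline total bilirubin laboratory" value of at least 2 x ULN. There is no ALP condition, and each maximum is taken separately.

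The same section adds: "If participants have unscheduled laboratory results after Visit 4 that meet potential Hy's Law criteria, the participants will be included in analysis".

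SAP section 9.3.3 tabulates the criteria in Table C-2 and provides a listing of participants with hepatic abnormalities. Table C-2 has single-parameter rows for ALT, AST, ALT or AST, bilirubin and ALP. It then has two combined groups: concurrent elevations (ALT or AST at least 3 x ULN with bilirubin at least 1.5 or at least 2 x ULN) and potential Hy's law (the three-part criterion). Both combined groups point to one footnote: "Elevations are from the same day".

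**The concern.** The no-window definition is the one that the protocol itself labels as the evaluation of drug-induced serious hepatotoxicity. It allows for the two elevations falling on different days. A table that accepts only same-day pairs cannot reproduce that summary, so the reported number of combined cases could be lower than under the protocol's rule. Counts of this kind are expected to be close to zero, so a single case changes how the table reads. The SAP also gives no sign that the difference was intended.

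**Working it through.** The plan states no figure to reproduce. The check sets the rules side by side and applies them to invented laboratory profiles.

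**Rules.** For post-baseline draws on days d, in multiples of ULN, let L(d) be the larger of ALT and AST, B(d) total bilirubin and P(d) ALP.

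- SAP concurrent (2 x ULN row): some day d has L(d) >= 3 and B(d) >= 2.
- SAP potential Hy's law: some day d has L(d) >= 3, B(d) >= 2 and P(d) < 2.
- Protocol no-window: the maximum of L over all d is >= 3 and the maximum of B over all d is >= 2.

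Anyone who meets either SAP rule also meets the no-window rule. The reverse fails when the two maxima come from different days. With a single post-baseline draw, the SAP concurrent row and the no-window rule coincide.

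**Hypothetical profiles** (assumed values, not trial data). AST is 3 on day 4 and 2 on day 9, so ALT determines L throughout.

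| Profile | Draws | SAP Hy's law | SAP concurrent | Protocol no-window |
|---|---|---|---|---|
| A | Day 4: ALT 4, bilirubin 2.2, ALP 1 | yes | yes | yes |
| B | Day 4: ALT 4, bilirubin 1.1, ALP 1; day 9: ALT 2.5, bilirubin 2.2, ALP 1 | no | no | yes |
| C | Day 4: ALT 4, bilirubin 1.1, ALP 1; day 9: ALT 3.2, bilirubin 2.2, ALP 1 | yes | yes | yes |
| D | Day 4: ALT 4, bilirubin 2.2, ALP 2.5 | no | yes | yes |
| E | Day 4 only: ALT 4, bilirubin 1.1, ALP 1 | no | no | no |

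Profile B is the gap. Its maximum L is 4 and its maximum B is 2.2, so the no-window rule is met. On day 4 the bilirubin is 1.1, and on day 9 the ALT is 2.5, so no single day qualifies. Profile C shows that a later bilirubin rise is still counted if ALT remains at or above 3 x ULN.

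**Can profile B arise here?** Protocol section 8.2.4 schedules chemistry at Visits 1, 2 and 4, which gives one post-dose draw. The same section says that values considered clinically significant, during participation or within 30 days after the last dose, "should be repeated until the values return to normal or baseline or are no longer considered clinically significant by the investigator". Section 9.4.2.6 itself anticipates unscheduled results after Visit 4. Several post-dose draws in one participant are therefore foreseen, though not routine.

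**Is the definition elsewhere in the SAP?** Appendix B repeats the three-part criterion with its same-time wording. SAP section 9.2.5 tabulates events of special interest as flagged on the case report form, not from derived laboratory maxima. Appendix F covers imputation, Kaplan-Meier and baseline-covariate changes. The version history contains no hepatic entry.

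**The window.** Two draws on the same day always lie within 24 hours. Two draws 24 hours apart or less can fall either side of midnight, so the SAP footnote is slightly narrower than the protocol's window.

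**The case against.** The case for leaving the SAP alone has five parts.

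- **The protocol delegates.** Its section 9.4.2 says the safety analysis "will be fully defined in the SAP". That gives the SAP room to add detail. It does not explain the silent absence of a definition that the protocol had already written out.
- **Table specifications are separate.** SAP section 1.0 places them in another document, so the no-window table might be planned there. This stands as a limit: the documents show omission from the SAP text, not from the final outputs.
- **Appendix F starts from protocol version 1**, which is not available here, so that version may have lacked the rule. This too stands in part. However, the SAP's version history bases it on Amendment 2, and the Amendment 2 protocol contains the definition.
- **The affected participant remains visible.** This is correct. Profile B would appear in the ALT and bilirubin rows and in the hepatic listing, and could be reported as an event of special interest if flagged. Only the count as a combined case is lost.
- **Materiality is low.** Each participant is to receive one active 100 mg dose, and entry excludes ALT or AST above 1.5 x ULN. This stands.

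A reader might also infer more than the documents support. Not every delayed bilirubin rise is missed; profile C is counted. Not everyone with a raised ALT will have serial tests, because repeats depend on the investigator judging the value clinically significant, and section 8.2.4 does not say that a repeat must include bilirubin. The SAP is not less sensitive in every respect, since its row with bilirubin at 1.5 x ULN is broader than anything in Protocol 9.4.2.6. Nor does the SAP exclude late unscheduled results; section 9.3.3 counts any qualifying post-baseline value and does not address the point.

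**Conclusion.** The point holds in a limited form. The protocol plans a no-window summary, Table C-2 has no row that delivers it, and the SAP does not record the difference. The two documents give different counts only for a participant with post-baseline draws on at least two days, ALT or AST reaching 3 x ULN and bilirubin reaching 2 x ULN, and no single day on which both hold. The documents give no rate for such participants. With one scheduled post-dose draw and one active dose, few or none are to be expected. No efficacy result, sample size or error rate is affected. This is a free improvement that restores a planned safety summary, of nice-to-have severity. It rests on the SAP text alone, because the separate table specifications are not available.

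**What to change.** Make three edits to the SAP.

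1. Add a row to Table C-2, without the same-day footnote: maximum post-baseline ALT or AST >= 3 x ULN and maximum post-baseline total bilirubin >= 2 x ULN, no time window, no ALP condition.
2. State in section 9.3.3 that qualifying unscheduled results after Visit 4 are included, as in Protocol 9.4.2.6.
3. For the potential Hy's law row, replace the same-day footnote with the protocol's 24-hour window. The concurrent-elevation rows can keep the same-day rule.

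If the omission was deliberate, record and justify it in Appendix F instead. The cost is one row, one sentence and one footnote, with matching edits to the table specifications. No new data are needed.
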